# 4. SUBJECT ELIGIBILITY

Before any study-specific activities/procedure, written informed consent must be obtained (see Section 11.1). In addition to written informed consent from a legally acceptable representative, the assent of the child also must be obtained, as appropriate and if requested by the institutional review board/independent ethics committee (IRB/IEC).

Subjects from the cinacalcet arm of Study 20130356 or subjects in Study 20110100 who had their dose withheld at the EOIP visit, may enroll in this study if they meet eligibility criteria but will not restart dosing until the criteria for restarting dosing, defined in Section 6.2.3, are met.

Subjects who were  $\leq$  18 years old at week 20 in the 20130356 study or at the time of study termination, are eligible to enter this Study 20140159 even if they have already turned 18 years of age or are due to turn 18 years of age during their planned participation in the 20140159 study.

# 4.1 Inclusion and Exclusion Criteria

# 4.1.1 Inclusion Criteria

#### All Subjects

- 101 Subject's legally acceptable representative has provided informed consent when the subject is legally too young to provide informed consent and the subject has provided written assent based on local regulations and/or guidelines prior to any Study 20140159 activities/procedures being initiated.
- 102 Dialysate calcium concentration ≥ 2.5 mEq/L at day 1

All subjects with > 14 days between the last study visit in Study 20130356 or Study 20110100 and screening for Study 20140159

Page 21 of 79

#### 103 Subjects on anti-convulsant medication must be on a stable dose

#### All subjects from 20130356

- 104 Completed treatment through week 20 in the 20130356 study or on study at the time of Study 20130356 termination
- 105 Dry weight ≥ 12.5 kg at day 1 of Study 20140159

#### Subjects Randomized to the 20130356 Standard of Care Arm Only

- iPTH value  $\geq$  300 pg/mL (within 7 days of day 1 in Study 20140159)
- 107 Corrected calcium value ≥ 8.8 mg/dL within 7 days of day 1 in Study 20140159

#### All Subjects from 20110100

- 108 Completed week 26 End of Study visit in the, 20110100 study or on study at the time of Study 20110100 termination
- 109 Dry weight  $\geq$  7 kg at day 1 of Study 20140159

#### 4.1.2 Exclusion Criteria

General

Studies 20130356 or 20110100

- 201 Currently receiving treatment in another investigational device or drug study, or less than 30 days since ending treatment on another investigational device or drug study(s), other than Amgen Studies 20130356 or 20110100.
- 202 Other investigational procedures while participating in this study are excluded.
- 203 Malignancy except non-melanoma skin cancers, cervical or breast ductal carcinoma in situ within the last 5 years.
- 204 Subject has known sensitivity to any of the products to be administered during dosing.
- 205 Subject likely to not be available to complete all protocol-required study visits or procedures, and/or to comply with all required study procedures (eg, electronic patient diary [ediary]) to the best of the subject and investigator's knowledge
- 206 History or evidence of any other clinically significant disorder, condition or disease (with the exception of those outlined above) that, in the opinion of the investigator or Amgen physician, if consulted, would pose a risk to subject safety or interfere with the study evaluation, procedures, or completion.
- 207 Subject previously has entered this study.
- 208 If sexually active, subject is not willing to use acceptable contraception during treatment and for at least 9 days after the end of treatment.
- 209 Subject is pregnant or breast feeding, or planning to become pregnant during the study or within 9 days after the end of treatment
- 210 History of congenital long QT syndrome, second or third degree heart block, ventricular tachyarrythmias, or other conditions associated with prolonged QT interval

Page 22 of 79

211 A new onset of seizures or worsening of pre-existing seizure disorder

All Subjects with > 14 days between the last study visit in Study 20130356 or Study 20110100 and the screening visit in Study 20140159 will have the following exclusion criteria applied during screening and day 1:

- 212 Unstable chronic heart failure defined as worsening pulmonary edema or other signs and symptoms as per investigator assessment during screening
- 213 Received therapy with commercial cinacalcet after the last study visit in Study 20130356 or Study 20110100 before day 1 of Study 20140159
- 214 Scheduled date for kidney transplantation from a known living donor that makes completion of the study unlikely
- 215 Either new or recurrent cardiac ventricular arrhythmias requiring a change in treatment within 10 days prior to screening visit or day 1 of Study 20140159 screening
- 216 Hepatic impairment indicated by elevated levels of hepatic transaminase or bilirubin (aspartate aminotransferase [AST] ≥ 1.5 × upper limit of normal [ULN] OR alanine aminotransferase [ALT] ≥ 1.5 × ULN OR total bilirubin ≥ 1 × ULN per institutional laboratory range) during screening

#### All Subjects - Day 1 Study Visit

- 217 Subject has an ongoing adverse event from Studies 20130356 or 20110100 that is considered related to IP and:
  - Is ≥ CTCAE (v 4.0) grade 3, and/or
  - Considered clinically significant in the opinion of the investigator
- 218 Central laboratory values were not obtained/are not available at day 1 in Study 20140159
- 219 Corrected QT Interval (QTc) > 500 ms, using Bazett's formula
- 220 QTc ≥ 450 to ≤ 500 ms, using Bazett's formula, unless written permission to enroll is provided by the investigator after consultation with a pediatric cardiologist
- 221 Use of grapefruit juice, herbal medications, CYP3A4 inhibitors (eg, erythromycin, clarithromycin, ketoconazole, itraconazole), or CYP2D6 substrates (eg, flecainide, propafenone, metoprolol, desipramine, nortriptyline, clomipramine)
- 222 Use of concomitant medications that may prolong the QTc interval (eg, ondansetron, albuterol)

#### 5. SUBJECT ENROLLMENT

Before subjects begin participation in any study-specific activities/procedures, Amgen requires a copy of the site's written IRB/IEC approval of the protocol, informed consent form, and all other subject information and/or recruitment material, if applicable (see Section 11.2). Before commencement of study-specific activities/procedures the subject's legally acceptable representative(s) must personally sign and date the

Page 23 of 79

informed consent form, and the subject must personally sign and date the assent form as appropriate and if required by the IRB/IEC.

Subjects will retain the unique subject identification number received in studies 20130356 or 20110100. This number will be used to identify the subject throughout the clinical study and must be used on all study documentation related to that subject.

# 5.1 Screening

The screening period begins when the informed consent, and assent if applicable, is signed and concludes when the subject is either enrolled into the trial or screen failed. The informed consent can be signed up to 7 days ( $\pm$  3 days) prior to 20140159 day 1.

For subjects who do not meet the eligibility criteria in Section 4, re-screening will not be considered in this study.

# 5.2 Enrollment

Following confirmation that subjects met eligibility criteria in Section 4, the subject will be registered in the interactive voice response/interactive web response (IVR/IWR) system. The subject will be considered enrolled in the extension study:

- 20130356 subjects will be assigned a cinacalcet dose based on the treatment arm and/or last dose received in Study 20130356 following the dosing instructions in Section 6.2.3.
- 20110100 subjects will be assigned a cinacalcet dose based on the last dose received at the EOIP visit in Study 20110100 following the dosing instructions in Section 6.2.3.

#### 6. TREATMENT PROCEDURES

#### 6.1 Standard of Care

Standard of care therapy will include the use of vitamin D sterols, calcium supplementation, and phosphate binders.

Standard of care therapy that is commercially available will not usually be provided or reimbursed by Amgen (except if required by local regulation). The Investigator will be responsible for obtaining supplies of these therapies unless they are provided by Amgen.

# 6.2 Cinacalcet

#### 6.2.1 Classification of Product

The Investigational Product Instruction Manual (IPIM), a document external to this protocol, contains detailed information regarding the storage, preparation, and administration of cinacalcet.

# 6.2.2 Investigational Product

Cinacalcet will be manufactured and packaged by Amgen Inc., or designee, and distributed using Amgen clinical study drug distribution procedures. Cinacalcet will be provided as capsules or as film coated tablets and will be orally administered daily. For subjects unable to swallow, the dose of cinacalcet may be administered via their feeding tube using the liquid suspension.

#### **Capsules**

Each capsule will contain 5 mg of cinacalcet in addition to the following inactive excipients: microcrystalline cellulose, pregelatinized starch, povidone, crospovidone, and colloidal silicon dioxide. Cinacalcet capsules will be provided in bottles containing 10 capsules each. The capsules provided must not be swallowed whole. Capsules must be opened and either sprinkled onto soft food (eg, applesauce) or suspended into a sucrose syrup to create a liquid suspension for administration. Once opened, the empty capsule shells should be discarded.

#### Tablets

Tablets will be provided in bottles containing 10 tablets of cinacalcet in a strength of 30 mg. Tablets of cinacalcet are to be swallowed whole and contain the following inactive excipients in addition to cinacalcet: microcrystalline cellulose, pregelatinized starch, povidone, crospovidone, colloidal silicon dioxide, and magnesium stearate. Each tablet is color-coated with Opadry II (green) and Opadry clear coatings then covered with carnauba wax.

#### 6.2.3 Dosage, Administration, and Schedule

Cinacalcet will be administered daily. All doses are to be taken orally and administered with food or shortly after a meal at the same time each day. For subjects unable to swallow, cinacalcet may be administered via their feeding tube using the liquid suspension. It is expected that for children under the age of 12 the daily administration of cinacalcet will be under the supervision of their parent(s) or legal guardian(s). On

CONFIDENTIAL

Page 24 of 79

Page 26

Page 25 of 79

study visit days where a blood sample is to be drawn, cinacalcet should not be

administered until after the blood sample has been obtained.

The protocol-specified doses (PSD) for use in this study are:

- Subjects ≥ 6 years of age: 2.5, 5, 10, 15, 30, 60, 90, 120, and 180 mg. Subjects from Study 20130356 will either continue to receive cinacalcet at the same dose as at the EOIP visit if ≤ 14 days have passed between last dose of cinacalcet treatment in Study 20130356 and day 1 of Study 20140159. If > 14 days have passed, subjects will start cinacalcet in Study 20140159 at 0.20 mg/kg/day based on the subject's dry weight at Study 20140159 day 1 time point and age at time of enrollment in Study 20130356, rounded down to the lowest PSD.
  - Subjects from 20130356 may receive capsules for any dose which is an exact multiple of 5 mg. Subjects who are assigned doses of 60 to 180 mg/day will require administration of two to six 30 mg tablets per dose. For those subjects unable to swallow tablets, capsules may be dispensed.
  - The maximum dose of cinacalcet that will be administered at any time during the study will be 2.5 mg/kg/day based on the subject's day 1 dry weight in Study 20140159 or 180 mg daily, whichever is lower.
- Subjects < 6 years of age: 1, 2.5, 5, 7.5, 10, 15, 30, and 60 mg. Subjects from Study 20110100 will either continue to receive cinacalcet at the same dose as at the EOIP visit if ≤ 14 days have passed between last dose of cinacalcet treatment in Study 20110100 and day 1 of Study 20140159. If > 14 days have passed, subjects will start cinacalcet in Study 20140159 at 0.20 mg/kg/day based on the subject's dry weight at the 20140159 day 1 time point and age at time of enrollment in 20110100 study, rounded down to the lowest PSD.
  - Subjects assigned a dose between 10 to 60 mg/day will require more than 1 capsule per dose be sprinkled on soft food or used to create the liquid suspension for administration.
  - Subjects enrolling into 20140159 from 20110100 would have a maximum dose of 2.5 mg/kg/day based on the subject's 20140159 day 1 dry weight or 60 mg daily, whichever is lower.

Subjects will be required to return all unused medication, including empty bottles, at each study visit. Site staff will confirm that the previously assigned medication bottle(s) have been returned prior to dispensing a new bottle(s) of IP. In the event unused medications or empty bottles have been permanently misplaced, contact Amgen prior to dispensing new bottle(s) of IP.

If no ionized calcium values are available at the time of a study visit, a new bottle of IP will not be dispensed to the subject. Once the ionized calcium value has been obtained and in accessible range, IP may be dispensed as appropriate.

AMGEN

#### 6.2.3.1 Dosage Adjustments, Delays, Rules for Withholding or Restarting, Permanent Discontinuation

Dosage adjustments, titrations, and withholding/restarting rules will be the same as the parent studies.

# 6.2.3.1.1 Subjects From Study 20130356

On day 1 of Study 20140159, subjects from the SOC arm in 20130356 will receive the initial dose of cinacalcet as defined in Section 6.2.3.1.1.1

Subjects from the cinacalcet arm with  $\leq$  14 days between last dose of cinacalcet treatment in Study 20130356 and Study 20140159 day 1 will continue at the same dose as the last dose at EOIP and will follow the dose adjustments outlined in Table 1 in Section 6.2.3.1.1.1. Dose titration cannot occur until week 4 per Table 1. If subjects from the cinacalcet arm in 20130356 are on a dose that was withheld or missed for > 14 days and  $\leq$  1 month at day 1 of Study 20140159, the iPTH and cCa restart values (iPTH > 150 pg/mL and cCa > 8.4 mg/dL) must be reached prior to resuming cinacalcet will receive the initial dose of cinacalcet in the current extension study outlined in Table 1 in Section 6.2.3.1.1.1.

Subjects from the cinacalcet arm with > 1 month between the last dose of cinacalcet treatment in Study 20130356 and Study 20140159 day 1, will receive the initial dose of cinacalcet as defined in Section 6.2.3.1.1.1. To commence dosing, all subjects must have:

- ionized calcium  $\geq$  1.05 mmol/L prior to initiation of treatment on day 1 in this study
- iPTH value ≥ 300 pg/mL within 7 days of day 1
- corrected calcium value ≥ 8.8 mg/dL within 7 days of day 1

#### 6.2.3.1.1.1 Dosage Adjustments

The initial dose of cinacalcet and all subsequent doses will be calculated by the site staff and confirmed by the IVR/IWR system. Subjects from the SOC arm will start at the initial cinacalcet dose of 0.20 mg/kg/day, based on the subject's dry weight at day 1 of Study 20140159, rounded down to the lowest PSD.

Subjects from the cinacalcet arm with  $\leq$  14 days between the last dose of cinacalcet treatment in Study 20130356 and day 1 of Study 20140159 will start cinacalcet dosing at the same dose they received at the completion of the EOIP visit and follow weekly dose adjustment based on the Table 1. For subjects from the cinacalcet arm with > 14 days between the last dose of cinacalcet treatment in Study 20130356 and day 1 of

AMGEN

Page 26 of 79

Page 27 of 79

Study 20140159, the initial dose of cinacalcet will be 0.20 mg/kg/day, based on the subject's dry weight at day 1 of 20140159, rounded down to the lowest PSD, will be assigned.

Dose adjustments for subjects receiving cinacalcet will be assessed at each weekly visit during the treatment period. The daily dose of cinacalcet may only be increased at monthly titration visits (week 4, 8, 12, 16, 20, and 24); it can't be increased at any other time during the treatment period. At all weekly visits (including week 4, 8, 12, 16, 20, and 24), the dose may be maintained, reduced or withheld based upon the dose adjustment criteria in Table 1.

If any of the criteria for dose withholding are met at any time during the trial, including between scheduled study visits (ie, unscheduled), the dose of cinacalcet is to be withheld until all of the following criteria are met:

- central laboratory corrected calcium value is >8.4 mg/dL
- iPTH is > 150 pg/mL
- ionized calcium is >1.05mmol/L
- subject has no symptoms of hypocalcemia
- subject doesn't have any ongoing adverse event(s) which warrant withholding of cinacalcet.

If a subject dose is being withheld, ionized calcium levels should be assessed weekly until an ionized calcium of >1.05 mmol/L is obtained, at which point, cCa and iPTH should be assessed by the central laboratory.

Once all the restart criteria above are met, cinacalcet may be restarted at one PSD below the previous dose received. Subjects receiving the lowest PSD (2.5 mg) who require a dose reduction will have their dose withheld until the criteria for maintaining or increasing the dose are met, at which time they will restart dosing at 2.5 mg/day.

If subjects require temporary administration of concomitant medications that are known to prolong the QTc interval, are CYP3A4 inhibitors, or are CYP2D6 substrates, the administration of IP is to be withheld. The dose may be restarted at one PSD below the previous dose once the treatment with the concomitant medication has completed and all of the restart criteria above are met.

If IP has been withheld or missed for > 14 days, the subject will resume dosing at the starting dose level once (initial dose in parent Studies 20130356 or 20110100) all restart criteria are met based on dry weight at day 1 of Study 20140159.

AMGEN

Page 28 of 79

If any of the criteria for dose decrease are met between scheduled study visits, the dose of cinacalcet is to be suspended until the next visit at which time the dose will be decreased per dose adjustment procedures of that visit.

CONFIDENTIAL

Product: Cinacalcet HCI Protocol Number: 20140159 Date: 01 June 2016 Page 29 of 79

	Monthly Dose Titration Visit Rules (Weeks 4, 8, 12, 16, 20, 24)				Weekly Dose Adjustment Visit Rules (Weeks 1, 2, 3, 5, 6, 7, 9, 10, 11, 13, 14, 15, 17, 18, 19, 21, 22, 23, 25, 26, 27)			Dose Withholding for Safety at Any Time (Monthly, Weekly or Unscheduled)
	↑ one PSD	Maintain Dose	↓ one PSD**	withhold*	Maintain Dose	↓ one PSD**	withhold*	withhold*
	(if all c riteria met)	(if al l criteria met)	(if any criteria met)	(if any criteria met)	(if al l criteria met)	(if any criteria met)	(if any criteria met)	(if any criteria met)
Corrected Calcium (central laboratory)	≥ 8.4 mg/dL	≥8.4 mg/dL	≥ 8.0 - < 8.4 mg/dL	< 8.0 mg/dL	≥ 8.4 mg/dL	≥ 8.0 - < 8.4 mg/dL	< 8.0 mg/dL	< 8.0 mg/dL
	(≥ 2.1 mmol/L)	(≥2.1 mmol/L)	(≥ 2.0- < 2.1 mmol/L)	(< 2.0 mmol/L)	(≥ 2.1 mmol/L)	(≥ 2.0- < 2.1 mmol/L)	(< 2.0 mmol/L)	(< 2.0 mmol/L)
Ionized Calcium	≥ 1.05 mmol/L	≥ 1.05 mmol/L	≥ 1.00 - < 1.05 mmol/L	< 1.00 mmol/L	≥ 1.05 mmol/L	≥ 1.00 - < 1.05 mmol/L	< 1.00 mmol/L	< 1.00 mmol/L
Total Calcium (local laboratory)	N/A	N/A	N/A	< 8.0 mg/dL (< 2.0 mmol/L)	N/A	N/A	< 8.0 mg/dL (< 2.0 mmol/L)	< 8.0 mg/dL (< 2.0 mmol/L)
iPTH	≥ 300 pg/mL	≥ 150 - < 300 pg/mL	≥ 100 - < 150 pg/mL	< 100 pg/mL	≥ 150 pg/mL	≥ 100 - < 150 pg/mL	< 100 pg/mL	< 100 pg/mL
	(≥ 31.8 pmol/L)	(≥ 15.9 - < 31.8 pmol/L)	(≥ 10.6 - < 15.9 pmol/L)	(< 10.6 pmol/L)	(≥ 15.9 pmol/L)	(≥ 10.6 - < 15.9 pmol/L)	(< 10.6 pmol/L)	(< 10.6 pmol/L)
Symptoms of Hypocalcemia	None	None	N/A	Yes	None	N/A	Yes	Yes
Other AE that warrants IP dose withhold	None	None	N/A	Yes	None	N/A	Yes	Yes

#### Table 1. Dose Adjustment Rules: Monthly, Weekly, and Withholding in Children 6-18 Years of age

\* restart one PSD below last dose when cCa is > 8.4 mg/dL, iPTH is > 150 pg/mL, ionized calcium is > 1.05 mmol/L, symptoms of hypocalcemia and other AE that warrants IP dose withholding have resolved.

\*\* if any lab values that warrant a dose decrease are received between regularly scheduled visits, the subject dose should be suspended until the next visit, at which time the dose will be decreased per dose adjustment procedures of that visit.

# 6.2.3.1.2 Subjects From Study 20110100

For subjects where the last dose of cinacalcet treatment in Study 20110100 and day 1 of Study 20140159 occurs within 14 days, in order to commence dosing, subjects from Study 20110100 will follow the weekly dose adjustment criteria as outlined in Table 2 for age < 2 years and Table 3 for age  $\geq$  2 years. Dose titration cannot occur until week 4.

For subjects with > 14 days and < 1 month between last dose of cinacalcet treatment in Study 20110100 and day 1 of Study 20140159, in order to commence dosing at the initial dose, all subjects from Study 20110100 must meet restart criteria per weekly dose adjustment criteria as outlined in Table 2 for age < 2 years and Table 3 for age  $\geq$  2 years. Dose titration cannot occur until week 4.

- Additionally the phosphorus value within 7 days of day 1 should be:
  - ≥ 5.0 mg/dL (1.25 mmol/L) if age is < 1 year

  - $\ge 4.5 \text{ mg/dL} (1.13 \text{ mmol/L}) \text{ if age is } \ge 1 \text{ year}$

For subjects with > 1 month between last dose of cinacalcet treatment in Study 20110100 and day 1 of Study 20140159, in order to commence dosing, subjects from Study 20110100 must have:

- ionized calcium prior to initiation of treatment on day 1 in this study
  - $\ge 1.13 \text{ mmol/L}$  if age is < 2 years
  - ≥ 1.05 mmol/L if age is ≥ 2 years
- iPTH value ≥ 300 pg/mL within 7 days of day 1
- corrected calcium value within 7 days of day 1
  - ≥ 9.4 mg/dL if age is < 2 years

  - $\ge 8.8 \text{ mg/dL}$  if age is  $\ge 2 \text{ years}$
- phosphorus value within 7 days of day 1
  - ≥ 5.0 mg/dL (1.25 mmol/L) if age is < 1 year

  - ≥ 4.5 mg/dL (1.13 mmol/L) if age is ≥ 1 year

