#### 3.2 Number of Sites

This study will be conducted at approximately 60 sites in North America, Europe, Russia, Latin America, and Australia.

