#### 6.2.3.1.2.1 Subjects < 2 Years of Age

The initial dose of cinacalcet and all subsequent doses will be calculated by the site staff and confirmed by the IVR/IWR system.

For subjects with > 14 days since the last dose of cinacalcet treatment in Study 20110100 and day 1 of Study 20140159, subjects will start at the initial cinacalcet dose of 0.20 mg/kg/day, based on the subject's dry weight at day 1, in the 20140159 study rounded down to the lowest PSD.

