Page 32 of 79

If IP has been withheld or missed for more than 14 days, the subject will resume dosing at the starting dose level (initial dose in parent Studies 20130356 or 20110100) once all restart criteria are met.

If any of the criteria for dose decrease are met between scheduled study visits, the dose of cinacalcet is to be suspended until the next visit at which time the dose will be decreased per dose adjustment procedures of that visit.

CONFIDENTIAL

	Monthly Dose Titration Visit Rules (Weeks 4, 8, 12, 16, 20, 24)				Weekly Dose Adjustment Visit Rules (Weeks 1, 2, 3, 5, 6, 7, 9, 10, 11, 13, 14, 15, 17, 18, 19)			Dose Withholding for Safety at Any Time (Monthly, Weekly or Unscheduled)
	↑ one PSD	Maintain Dose	↓ one PSD**	withhold*	Maintain Dose	↓ one PSD**	withhold*	withhold*
	(if all c riteria met)	(if al l criteria met)	(if any criteria met)	(if any criteria met)	(if al l criteria met)	(if any criteria met)	(if any criteria met)	(if any criteria met)
Corrected Calcium (central laboratory)	≥ 9.0 mg/dL	≥ 9.0 mg/dL	≥ 8.6 - < 9.0 mg/dL	< 8.6 mg/dL	≥ 9.0 mg/dL	≥ 8.6 - < 9.0 mg/dL	< 8.6 mg/dL	< 8.6 mg/dL
	(≥ 2.25 mmol/L)	(≥ 2.25 mmol/L)	(≥ 2.15 - < 2.25 mmol/L)	(< 2.15 mmol/L)	(≥ 2.25 mmol/L)	(≥ 2.15 - < 2.25 mmol/L)	(< 2.15 mmol/L)	(< 2.15 mmol/L)
lonized Calcium	≥ 1.13 mmol/L	≥ 1.13 mmol/L	≥ 1.08 - < 1.13 mmol/L	< 1.08 mmol/L	≥ 1.13 mmol/L	≥ 1.08 - < 1.13 mmol/L	< 1.08 mmol/L	< 1.08 mmol/L
Total Calcium (local aboratory)	Not Applicable	< 8.6 mg/dL (< 2.15 mmol/L)	Not Applicable	< 8.6 mg/dL (< 2.15 mmol/L)	< 8.6 mg/dL (< 2.15 mmol/L)	Not Applicable	< 8.6 mg/dL (< 2.15 mmol/L)	< 8.6 mg/dL (< 2.15 mmol/L)
PTH	≥ 300 pg/mL 31.8 pmol/L)	≥ 150 - < 300 pg/mL (≥ 15.9 - < 31.8 pmol/L)	≥ 100 - < 150 pg/mL (≥ 10.6 - < 15.9 pmol/L)	< 100 pg/mL (≥ (< 10.6 pmol/L)	≥ 150 - < 300 pg/mL (≥ 15.9 - < 31.8 pmol/L)	≥ 100 - < 150 pg/mL (≥ 10.6 - < 15.9 pmol/L)	< 100 pg/mL (< 10.6 pmol/L)	< 100 pg/mL (< 10.6 pmol/L)
Symptoms of Hypocalcemia	None	None	N/A	Yes	None	N/A	Yes	Yes
Other AE that warrants IP dose withhold	None	None	N/A	Yes	None	N/A	Yes	Yes

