#### 7.3.11 Laboratory Assessments

All study laboratory samples, with the exception of the ionized calcium samples, will be processed and sent to the central laboratory for assessment. The central laboratory will provide a study manual that outlines handling, labeling, and shipping procedures for all blood samples. All blood samples will be obtained via venipuncture prior to the administration of IP. The date and time of the sample collection will be recorded in the source documents at the site.

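### The phosphorus limits for restarting cinacalcet in children from Study 20110100 are converted to mmol/L with the calcium factor, so the two printed units set different cut-offs

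*Protocol*

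**What the plan says.** Section 6.2.3.1.2 of the protocol divides children from Study 20110100 by the time since their last dose in that study. Those within 14 days follow the weekly rules of Table 2 or Table 3. The next group is introduced with "For subjects with > 14 days and < 1 month between last dose of cinacalcet treatment in Study 20110100 and day 1 of Study 20140159", and a third group has a gap of more than one month. For both of the longer gaps, phosphorus measured within 7 days of day 1 must reach a minimum. For infants it is "≥ 5.0 mg/dL (1.25 mmol/L) if age is < 1 year". For children aged 1 year or more it is 4.5 mg/dL, with 1.13 mmol/L in brackets. The pair of limits is printed twice, once per group, which makes four mmol/L values.

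The calcium limits are also printed in both units. Table 1 has "< 8.0 mg/dL (< 2.0 mmol/L" as a withholding limit and Table 2 has "< 8.6 mg/dL (< 2.15 mmol/L".

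On measurement and dosing, Section 7.3.11 states: "All study laboratory samples, with the exception of the ionized calcium samples, will be processed and sent to the central laboratory for assessment". Section 6.2.3.1.2.1 states: "The initial dose of cinacalcet and all subsequent doses will be calculated by the site staff and confirmed by the IVR/IWR system". The reporting unit for phosphorus is not given.

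**The concern.** The factor that turns mg/dL into mmol/L depends on the molar mass of the analyte. Calcium and phosphorus have different molar masses and cannot share a factor, yet the phosphorus limits appear to use the calcium one. If so, the bracketed figure does not restate the limit in other units. It is a second, looser limit.

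The limit decides whether dosing may begin, and it applies to children who were under 6 years old when they entered the parent study. Section 3.2 describes the geography: "This study will be conducted at approximately 60 sites in North America, Europe, Russia, Latin America, and Australia". With that spread, some sites are likely to work in mmol/L, although the documents do not say which. Two children with the same phosphorus could then be treated differently, and a child well below the mg/dL limit could be started on drug.

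**Working it through.** **Inputs**
- Phosphorus limits, Section 6.2.3.1.2: 5.0 mg/dL printed as 1.25 mmol/L; 4.5 mg/dL printed as 1.13 mmol/L.
- Calcium limits, Tables 1 to 3: 8.0, 8.4, 8.6 and 9.0 mg/dL printed as 2.0, 2.1, 2.15 and 2.25 mmol/L.
- Molar masses, which are physical constants not printed in the documents: phosphorus 30.974, calcium 40.078, phosphate ion 94.97 g/mol.

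**Formula:** mmol/L = mg/dL × 10 / molar mass.

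**Step 1. Factor implied by the printed figures**
- Calcium: 2.0/8.0 = 2.1/8.4 = 2.15/8.6 = 2.25/9.0 = 0.25.
- Phosphorus: 1.25/5.0 = 0.250; 1.13/4.5 = 0.251.

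**Step 2. Which factor reproduces the printed phosphorus figures**

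| Factor | 5.0 mg/dL | 4.5 mg/dL | Matches 1.25 and 1.13? |
|---|---|---|---|
| Protocol's calcium factor, 0.25 | 1.250 | 1.125 (rounds to 1.13) | Yes, both |
| Phosphorus, 10/30.974 = 0.3229 | 1.614 | 1.453 | No |
| Phosphate ion, 10/94.97 = 0.1053 | 0.526 | 0.474 | No |

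The exact calcium factor, 10/40.078 = 0.2495, gives 1.248 and 1.123. The printed 1.13 therefore points to the rounded 0.25. The protocol does convert iPTH with its own factor (300 pg/mL printed as 31.8 pmol/L, or 0.106), so one factor for all analytes is not its convention.

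**Step 3. Printed mmol/L limits read back as phosphorus**
- 1.25 × 3.0974 = 3.87 mg/dL. This is 5.0 − 3.87 = 1.13 mg/dL too low, or 1.13/5.0 = 22.6%.
- 1.13 × 3.0974 = 3.50 mg/dL. This is 4.5 − 3.50 = 1.00 mg/dL too low, or 1.00/4.5 = 22.2%.

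**Step 4. Range in which the two units disagree**
- Under 1 year: 3.87 to below 5.0 mg/dL (1.25 to below 1.61 mmol/L).
- 1 year and over: 3.50 to below 4.5 mg/dL (1.13 to below 1.45 mmol/L).

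Throughout both ranges the child passes the mmol/L limit and fails the mg/dL limit.

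**The case against.** The arithmetic is not in dispute. The case on the other side concerns reach and consequence.

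- **Reach.** The rule binds only after more than 14 days off drug. SAP Section 3.2 plans on 30 subjects from Study 20110100, and the 7 kg minimum weight in Section 4.1.1 probably leaves few infants under 1 year. This stands as a limit on numbers. The group need not be empty, however. Sections 2.5.2 and 3.1.2 give completers 24 weeks of treatment, with extension day 1 at week 26, so the nominal gap is 14 days. A visit one day late crosses the line, and so may an administrative delay.
- **Working unit.** Phosphorus is measured centrally, mg/dL is printed first, and the corrected calcium limits in the list for gaps over one month appear in mg/dL only. The sites may all work in mg/dL. That is possible, but the documents do not say so. Central measurement does not cure the error if the result is reported in mmol/L. Confirmation by IVR/IWR does not cure it either, since the documents do not say whether that system checks phosphorus, and a check built from this text could carry the same error.
- **Safety.** Hypocalcemia is the dosing hazard that the protocol stresses. The calcium, iPTH and symptom rules still apply, a restarting child receives only 0.20 mg/kg/day, and ionized calcium is checked weekly. Tables 1 to 3 contain no phosphorus rule. The list for the shorter gap is also worded less strictly than the one for the longer gap. All this lowers the likely harm. It also means that no dose-adjustment table applies a phosphorus limit later on.
- **Inference.** The study is descriptive and phosphorus is not an inclusion criterion, so no planned estimate is materially at risk. This stands. The defect lies in a dosing rule and does not affect the analysis.

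**Conclusion.** The concern holds. All four printed mmol/L phosphorus limits in Section 6.2.3.1.2 use the calcium factor. They are looser than the mg/dL limits beside them by 1.13 mg/dL (23%) in infants and 1.00 mg/dL (22%) in older children. The current protocol text neither corrects this nor names a governing unit, so the condition for dosing has two meanings.

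The result rests on the molar mass of phosphorus and on reading the limits as elemental phosphorus; reading them as phosphate ion does not reproduce the printed figures either. That a site compares in mmol/L is an assumption, and actual misdosing is possible but not shown. The affected group is children from Study 20110100 who are more than 14 days off drug. Because the rule controls dosing in young children and is cheap to correct, it should be put right despite the small numbers.

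**What to change.** The clinical team should first state which limit is intended. If mg/dL governs, print 1.61 mmol/L beside 5.0 mg/dL and 1.45 mmol/L beside 4.5 mg/dL in both lists of Section 6.2.3.1.2. If the mmol/L figures were intended, the mg/dL figures become about 3.87 and 3.50.

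Confirm that the IVR/IWR system and any site worksheets hold the same single value, and find out which unit the central laboratory reports. Until the amendment is in force, send sites a letter giving the correct limit in both units.

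The cost is four printed values in an administrative amendment, one configuration check and a letter. There is no effect on data collection, analysis or sample size.
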